## **6.8. Handling of Missing Data**

### **6.8.1. Missing Efficacy Endpoints**

For the primary endpoint, sensitivity analyses with missing data being imputed will be conducted to support the robustness of the analysis result. The base imputation scenario will be based on an ANCOVA model with the MAR-based multiple imputation (Rubin 1987) for all missing ALSFRS-R total scores, and imputation will be performed for each randomized treatment group separately. Imputation based on the distribution of ALSFRS-R total score in the placebo group will also be performed for both reldesemtiv and placebo groups.

Tipping point analyses will be conducted by setting the imputed values for the deaths successively worse only for the reldesemtiv group while maintaining the MAR-based imputed values for the placebo group. Imputation by setting the imputed values successively worse for data missing due to any reasons in the reldesemtiv group will also be performed.

For the first secondary endpoint, sensitivity analyses will be conducted with imputing ALSFRS-R total scores based on the distribution of that in the placebo group. Tipping point analyses will be performed by setting the imputed values successively worse only for the reldesemtiv group while maintaining the MAR-based imputed values for the placebo group.

### **6.8.2. Missing Start and Stop Dates for Prior and Concomitant Medication**

Imputation of missing/partial dates will not be performed. The available year or year and month in a partial date will be used and will be compared to first dosing year, month and day to determine whether to include the medication in the medication history or as a concomitant medication. If the available data do not give sufficient information to classify the medication, the medication will be classified as concomitant medication.

### **6.8.3. Missing Start and Stop Dates for Adverse Events**

For AEs with incomplete date information recorded in the eCRF, the imputation will follow the following algorithm:

For missing AE onset Day and Time:

- If an AE onset Day is missing and the Month of AE onset is known, then the first day of the month of AE onset will be imputed as the AE onset date.
- If AE onset information is not available, then the first dosing date will be imputed as the AE onset date.

For missing AE end Day and Time:

- If the AE end Day is missing and the AE end Month is earlier or later than that of the Follow-Up Visit, then the last day of the AE end month will be the imputed as the AE end date.

- If the AE end Day is missing and the AE end Month is the same as that of the Follow-Up Visit, then the date of the Follow-Up Visit will be the imputed as the AE end date.
- If no AE end information is available, then
  - For patients who discontinued early from study drug, the imputed AE end date will be on the later of the last dosing date + 28 days or the last visit or contact date.
  - For patients who completed the study, the imputed AE end date and time will be the date of the Follow-Up Visit.
  - If the stop date is missing and the event is ongoing, the event will be noted as ongoing” in the stop date column in data listings.

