8.3.1.6. Reporting of AEs

The investigator is responsible for ensuring that all adverse events observed by the investigator or reported by the patient that occur after starting the study drug through end of study are recorded in the AE CRF. In addition, during the screening period (after signing of the informed consent until study drug administration), serious adverse events considered related to study procedures are also to be recorded in the AE CRF.

ALS is a progressive and uniformly fatal neurodegenerative disorder associated with relentlessly progressive loss of motor function, including appendicular, craniobulbar, and respiratory function due to the degeneration of the upper and lower motor neurons which control and innervate the voluntary skeletal muscles. The following conditions are anticipated to occur in the study population as signs/symptoms of ALS progression and do not need to be recorded as an AE unless they meet the criteria for an SAE, are felt to be related to the study drug, or they are occurring outside what is expected for the normal course of the disease ([Brown 2017](#)).

Table 4: Signs and Symptoms Commonly Associated with ALS

MedDRA Preferred Term ^a	MedDRA Preferred Term ^a
Dysarthria	Muscle spasticity
Dysphagia	Muscle contractions involuntary
Dyspnoea	Muscle spasms
Gait disturbance	Muscular weakness

^a MedDRA Version 23.0

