### **6.7.2. Study Day**

If the date of interest occurs on or after the first dose date, then study day will be calculated as (date of interest – date of first dose) + 1. If the date of interest occurs prior to the first dose date, then study day will be calculated as (date of interest – date of first dose). There is no study day 0.

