## **9. SAFETY AND TOLERABILITY**

Safety and tolerability analyses will be based on the Safety Analysis Set. Safety data will be analyzed descriptively and tabulated by the early-start and delayed-start treatment groups for the double-blind placebo-controlled period and active drug period).

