#### **9.2.2. Missing and Partial AE Onset Dates**

For AEs with incomplete date information recorded on the eCRF, imputation will be performed following the algorithm below:

For missing AE onset Day and Time:

- If an AE onset Day is missing and the Month of AE onset is known, then the first day of the month of AE onset will be imputed as the AE onset date.
- If AE onset information is not available, then the first dosing date will be imputed as the AE onset date.

For missing AE end Day and Time:

- If the AE end Day is missing and the AE end Month is earlier or later than that of the Follow-Up Visit, then the last day of the AE end month will be the imputed as the AE end date.
- If the AE end Day is missing and the AE end Month is the same as that of the Follow-Up Visit, then the date of the Follow-Up Visit will be the imputed as the AE end date.
- If no AE end information is available, then
  - For patients who discontinued early from study drug, the imputed AE end date will be on the later of the last dosing date + 28 days or the last visit or contact date.
  - For patients who completed the study, the imputed AE end date and time will be the date of the Follow-Up Visit.
  - If the stop date is missing and the event is ongoing, the event will be noted as ongoing” in the stop date column in data listings.

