### 9.4.1. Missing and Partial Concomitant and Other Medication Start and Stop Dates

Incomplete concomitant medication start and/or stop dates will be imputed as follows. If either the start of medication date is completely missing or the month and/or year of the start date is missing, the start date will be set to the first dose date. If only the day is missing, the day will be set to the first day of the month except if the start month is the same as the first dose month. If the latter is true, the start day will be set to the first dose day. No imputations will be applied to the stop date.

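### A missing AE onset day is set to the 1st of the month with no exception for the month of first dose, so an AE that began on treatment can be dated before dosing

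*SAP*

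**What the plan says.** SAP 6.8.3 covers an onset with a missing day and a known month: "then the first day of the month of AE onset will be imputed as the AE onset date". SAP 9.2.2 repeats the rule: "If an AE onset Day is missing and the Month of AE onset is known, then the first day of the month of AE onset" is the imputed onset. Neither section compares the result with the date of first dose. That date appears in the onset rule only for an AE with no onset date at all: "If AE onset information is not available, then the first dosing date will be imputed as the AE onset date".

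The concomitant-medication rule in SAP 9.4.1 also starts from the 1st of the month, but it applies "except if the start month is the same as the first dose month". For that case it continues: "If the latter is true, the start day will be set to the first dose day".

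Three other statements bear on the point:

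- **Collection (Protocol 8.3.1.6).** The investigator ensures that AEs "that occur after starting the study drug through end of study are recorded in the AE CRF". Before dosing, only serious AEs related to study procedures go there. Footnote 2 of the Schedule of Activities sends other pre-dose conditions to medical history.
- **Study day (SAP 6.7.2).** A date before first dose gets a negative study day. "There is no study day 0".
- **Reporting (SAP 9).** Safety data are "tabulated by the early-start and delayed-start treatment groups for the double-blind placebo-controlled period and active drug period". SAP 9.1 and 9.2.1 count treatment-emergent AEs (TEAEs).

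**The concern.** An ordinary AE on the AE form is, by the collection rule, one that began after study drug started. If its onset is in the first-dose month and the day is unknown, the imputation rule dates it before dosing unless dosing began on the 1st. The imputed date then contradicts what the record already establishes.

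The ordering of the cases points to an oversight. An AE with no onset information gets the first-dose date, which is compatible with treatment. An AE with a known month, which is better information, gets a date that is usually incompatible with it.

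What is at stake is the count of early TEAEs. If the programs flag treatment-emergence by comparing onset with first dose, as is usual, these AEs fall out of the TEAE summaries.

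**Working it through.** The documents give no figure for this rule, so there is none to reproduce. The check applies the rule literally.

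**Inputs.** The onset rule is from SAP 6.8.3 and 9.2.2, the study-day formula from SAP 6.7.2, and the Week 24 switch from the study design, taken as first dose + 168 days. Assumptions: first-dose days are uniform over the calendar, and AE onsets are uniform over the interval considered.

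**Step 1: one patient.** First dose 15 March 2022; AE onset recorded as March 2022, day unknown. The imputed onset is 1 March 2022. Study day = 1 March − 15 March = −14.

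**Step 2: how often the imputed date precedes dosing.** For first dose on day D of the month, the 1st precedes dosing whenever D > 1. In a 30-day month that is 29 of 30 values of D, or 96.7%. Applying the rule to 730 consecutive first-dose dates from 1 September 2021 also gives 96.7%. Over all those dates the imputed onset is on average 14.7 days before first dose, and at most 30.

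**Step 3: share of early AEs exposed to the problem.** Take onsets uniform over the first 28 days from first dose, in a 30-day month: 30 × 28 = 840 equally likely combinations.

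- The onset falls in the first-dose month when D plus the days elapsed is at most 30, giving min(28, 31 − D) onsets for each D.
- For D = 1, 2 and 3 this is 28 each, so 84. For D = 4 to 30 it is 27 + 26 + … + 1 = 378. The total is 84 + 378 = 462, and 462/840 = 55%.
- D = 1 causes no error, so remove its 28: 462 − 28 = 434, and 434/840 = 51.7%.

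So about 52% of AEs with onset in the first 28 days would be dated before dosing if their day were missing. This is a conditional share; the documents do not say how many AEs lack a day.

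**Step 4: effect of a guard.** If the first-dose date is used when the onset month and year match those of first dose, the share of start dates with a pre-dose imputed onset falls from 96.7% to 0%.

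**Step 5: the Week 24 switch month.** Let the switch fall on day D.

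- The current rule places every day-missing AE of that month in the double-blind period when D > 1. It is wrong for AEs that began on or after the switch: the average over D of (31 − D)/30 for D = 2 to 30 is 435/900 = 48.3%. The 730-date run gives 48.4%.
- Imputing the switch date would be wrong for AEs that began before the switch: the average of (D − 1)/30 is 14.5/30 = 48.3%.

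The two error rates are the same and only the direction changes.

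**The case against.** The strongest reply is that the harm is inferred. Neither document defines treatment-emergent by date. Because collection starts with study drug, a programmer could treat every ordinary AE on the form as on treatment whatever its imputed date. That stands: loss from the TEAE tables is conditional on an onset-date definition. It does not rescue the imputed date, which is still wrong and still gives a negative study day.

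A reader might infer more than the text supports, in three ways.

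- **That all main safety tables are affected.** SAP 9.2.3 summarises serious AEs and AEs leading to discontinuation or death, and SAP 9.2.4 summarises AEs of special interest, without a stated restriction to treatment-emergent events. SAP 9.2.1 lists all AEs.
- **That early eGFR and bilirubin signals would be lost.** Those early findings come from the Phase 2 trial (Protocol 2.3.1). Here SAP 9.5 analyses renal and liver results from dated laboratory data. Renal and hepatic AEs of special interest must be reported within 24 hours of awareness (Protocol 7.3 and 7.4), so they are among the least likely to lack an onset day.
- **That the rule wrongly credits reldesemtiv-period AEs to placebo and must be changed at Week 24.** Some delayed-start AEs would be so placed. But the rule also moves early-start AEs into the double-blind period, and imputing the switch date misplaces just as many AEs the other way.

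Two further points stand. AEs are reviewed about every four weeks and SAP 6.3 provides edit checks and queries, so few onset days should be missing. And SAP 9.4.1 is an imperfect model, because SAP 6.8.2 says partial medication dates will not be imputed at all. The case for the guard does not rest on that comparison: the collection rule in Protocol 8.3.1.6 is enough.

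**Conclusion.** The point holds for the month of first dose. As written, SAP 6.8.3 and 9.2.2 give a post-dose AE with a missing day a pre-dose onset date on 29 of 30 first-dose days (97%), assuming these are uniform over a 30-day month. Nothing else in the SAP overrides the rule. Under the usual onset-based definition, which the documents do not state, such an AE would drop out of the TEAE tables.

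The absolute effect cannot be sized, because the number of AEs with a missing day is not given. It is probably small, and nothing in the documents shows that a headline safety result would change. No efficacy analysis is involved. The switch-month behaviour is a choice between two equal and opposite errors and is not a defect.

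**What to change.** In both SAP 6.8.3 and SAP 9.2.2, add: if the onset day is missing and the onset month and year are those of the first dose, impute the date of first dose, unless the recorded AE end date precedes first dose or the record is a screening serious AE related to study procedures. In those cases, and in every other month, keep the 1st of the month.

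This matches the guard in SAP 9.4.1. It costs one sentence in each section and slightly raises the TEAE count. It needs no new data and can be made before database lock, by which SAP Section 2 requires all final-analysis decisions. Stating in SAP Section 9 how treatment-emergent is determined would be a useful companion, since the effect of the imputed date depends on it.

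For the Week 24 switch month, leave the rule as it is. If wanted, add a sensitivity tabulation that imputes the switch date for day-missing AEs in that month, with its direction stated in advance. This is optional.

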## **7. STUDY POPULATION**

### **7.1. Subjects Disposition**

Count of patients in each analysis set will be presented. The count and percentage of patients who were randomized, who received at least one dose of study drug, who completed the study treatment at each study period, and who prematurely discontinued from the study drug and/or from the study at each study period will be presented by randomized treatment. Reasons for premature discontinuation will also be summarized.

All enrolled patients will be included in the listing of subjects disposition. In addition to patient ID, demographics (age, sex and race) and randomized treatment group, the listing will include screening date, first dose date, last dose date, last contact date, and reasons for discontinuation from the study treatment and/or from the study.

### **7.2. Screen Failures**

Screen failures will be listed and summarized by reasons of screening failure.

### **7.3. Protocol Deviations**

Protocol deviation is any divergence from the protocol that impacts a patient's safety, rights, or welfare or materially reduces the quality or completeness of the data. Patients meeting the protocol deviation criteria will be summarized by randomized treatment group and listed. The listing of protocol deviations will also include severity of deviation (major or minor) and indicate if a protocol deviation is COVID-19 related based on the reported data.

### **7.4. Demographic and Baseline Characteristics**

Demographic and baseline characteristics, including age, sex, race, ethnicity, height, weight, BMI, tobacco and alcohol use, etc., will be summarized by randomized treatment group for the FAS. All enrolled patients will be included in the listing of demographic and baseline characteristics.

### **7.5. Listing of Subject Inclusion and Exclusion Criteria**

A listing of randomized patients who violate the inclusion and exclusion criteria will be provided.

### **7.6. Medical History and Medical Conditions Present at Entry**

Medical history will be summarized by treatment received for the Safety Analysis Set. The count and percentage of patients with each medical history item will be presented by system organ class (SOC) and preferred term (PT). Listing of medical history and medical conditions present at entry will include each medical history item, start date, stop date, system organ class and preferred term.

Medical history of ALS will be summarized by treatment received for the Safety Analysis Set. The count and percentage of patients with or without family history of ALS or a known mutation in an ALS related gene, onset site of ALS, and the descriptive statistics of time since first

symptom onset and time since first diagnosis will be provided. Patient listing containing symptom onset date, and diagnosis date will be provided along with diagnostic time (time between onset of symptoms and diagnosis of ALS).

## **7.7. Prior Medication History and Medications Present at Entry**

### **7.7.1. Non-Diagnosis Related Prior Medication History**

Non-diagnosis related prior medication history will be summarized by treatment received for the Safety Analysis Set. Prior medication history and medication present at entry will be coded using World Health Organization (WHO) Drug Dictionary Enhanced with Herbal, B3, SEP 2020. The count and percentage of patients with each medication history item will be presented by therapeutic class (ATC Class 3) and preferred name. If ATC Class 3 is not available, ATC Class 2 will be used in the summary.

Listing of medication history will include each medication, start date, stop date, therapeutic class and preferred name.

### **7.7.2. Prior Diagnosis Related Medication History**

Prior diagnosis related medication history will be summarized by treatment received for the Safety Analysis Set. The count and percentage of patients who received riluzole and/or edaravone and who received the branded combination product of sodium phenylbutyrate and taurursodiol (also known as TUDCA, ursodoxicoltaurine or Tauroursodeoxycholic acid) will be presented.

## **7.8. Baseline Physical Examination**

Baseline physical examination results will be summarized for the Safety Analysis Set. Counts and percent of patients judged to be normal, abnormal, or not performed will be presented.

## **7.9. Baseline Vital Signs**

Baseline measurements of vital signs, such as heart rate, blood pressure, respiratory rate, weight, BMI and body temperature, will be summarized for the Safety Analysis Set.

## **7.10. Baseline Laboratory Data**

Baseline laboratory data, including hematology, serum chemistry and urinalysis, will be summarized for the Safety Analysis Set. The laboratory parameters to be included in the summary are listed in the protocol Appendix 2.

## **7.11. Baseline Primary and Secondary Efficacy Evaluations**

Baseline measurements of the primary and secondary efficacy analyses will be summarized by randomized treatment group for the FAS with appropriate descriptive statistics.

## **8. EFFICACY**

### **8.1. General Considerations**

Unless otherwise specified, inferential statistical tests will be two-sided and will be performed at alpha levels of 0.05 to declare the significance of effects.

### **8.2. Testing Statistical Assumptions Including Comparability at Baseline**

Assumptions for statistical models will be evaluated graphically. If assumptions are substantially violated, additional analysis methods will be performed. To assess the comparability of treatment groups, demographic and baseline characteristics will be compared between treatments for the FAS using Cochran-Mantel-Haenszel tests for binary categorical variables, van Elteren tests for ordinal categorical measures, or analysis of variance (ANOVA) for continuous variables, stratified by riluzole use and edaravone use at baseline.

### **8.3. Statement of the Null and Alternate Hypotheses**

The null hypothesis ( $H_0$ ) and alternative hypothesis ( $H_A$ ) for the primary and the first secondary endpoints are listed below:

For the primary endpoint:

$H_0$ : There is no treatment difference in the change from baseline to Week 24 in ALSFRS-R total score between patients randomized to placebo and those randomized to reldesemtiv during the double-blind, placebo-controlled period in the FAS.

$H_A$ : There is a treatment difference in the change from baseline to Week 24 in ALSFRS-R total score between patients randomized to placebo and those randomized to reldesemtiv during the double-blind, placebo-controlled period in the FAS.

For the first secondary endpoint:

$H_0$ : The Mann-Whitney probability of a more favorable status in either reldesemtiv or placebo group in the FAS is 0.5. The status is quantified by joint ranks based on the combined assessment of change in ALSFRS-R total score, time to dependence on assisted ventilation (either invasive or non-invasive), and survival time up to Week 24.

$H_A$ : The Mann-Whitney probability of a more favorable status in reldesemtiv group in the FAS is greater than 0.5. The status is quantified by joint ranks based on the combined assessment of change in ALSFRS-R total score, time to dependence on assisted ventilation (either invasive or non-invasive), and survival time up to Week 24.

### **8.4. Subgroup Analyses**

#### **8.4.1. Subgroups for Explanation of Potential Heterogeneous Treatment Effect**

Subgroup analyses with relatively moderate sample size will be performed to examine the consistency of the observed treatment effect and to gain insight into the effectiveness of reldesemtiv in subpopulations. Analyses of the primary endpoint and the first secondary endpoint will be conducted for the following subgroups:

- Sex (male, female)
- Age group (< median, ≥ median)
- Race (white, non-white)
- BMI at baseline (< 25 kg/m^2, ≥ 25 kg/m^2)
- Riluzole and edaravone use status at baseline (use riluzole, use edaravone, use neither).
- Percent predicted FVC at baseline (< median, ≥ median)
- ALSFRS-R total score at baseline (< median, ≥ median)
- Geographic region (North America, Europe, Australia)
- Anatomic site of disease onset (upper limb, lower limb, limb, bulbar, cognitive, respiratory)
- Time since ALS symptom onset (< 1.5 years, ≥ 1.5 years)
- Pre-study rate of disease progression (1st tertile, 2nd tertile, and 3rd tertile)
- MiToS at baseline (Stage 0, Stage 1, Stage 2, Stage 3 and Stage 4)

For the primary endpoint (ALSFRS-R total score change from baseline to Week 24):

- The MMRM with the subgrouping factors being added to the primary analysis model (see [Section 8.6.1](#)) will be used to produce treatment comparisons at each visit for each subgroup. The subgrouping factors include: the “subgroup” listed above as well as “subgroup-by-treatment”, “subgroup-by-visit”, and “subgroup-by-treatment-by-visit” interactions. If the MMRM fails to converge, an ANCOVA model with change from baseline to Week 24 as response variable and model terms listed as follows will be used to perform the analysis: treatment, baseline riluzole use, baseline edaravone use, baseline ALSFRS-R total score, covariates identified before the database lock (see [Section 8.6.1](#)), subgroup and subgroup-by-treatment interaction.

For the first secondary endpoint (combined assessment of change in ALSFRS-R total score, time to dependence on assisted ventilation (either invasive or non-invasive), and survival time up to Week 24):

- The joint rank test subsequent to the MAR imputation of missing ALSFRS-R total scores at Week 24 (see [Section 8.7.1](#)) will be applied for all subgroups.

